7.2 Statistical analysis

Psychometric assessment

Once completed questionnaires have been returned from family members recruited during the first month of recruitment (approximately 1000) and the data entered onto a secure database at the ICNARC CTU, a psychometric assessment of the FS-ICU will be rapidly undertaken. If results from the psychometric assessment demand substantive changes to the FS-ICU questionnaire, then these will be incorporated into a new version of the FS-ICU questionnaire and recruitment and data collection will re-commence and continue for 12 months.

The methods used in the psychometric assessment will mirror those employed in the North American validation study⁸ and utilise their FS-ICU scoring algorithm. The analysis will comprise the following steps: descriptive analysis; item reduction; factor analysis; reliability analysis; and validity analysis. Brief methods for each step are outlined below.

Descriptive analysis

Item descriptive statistics (percentage missing, percentage floor/ceiling scores, frequencies, median and interquartile range) will be computed for each site and all sites combined.

¹ FREE is recruiting family members for all patients staying 24 hours or more, however for the purpose of estimating targets we have excluded patients staying less than 36 hours - given family members of short term patients may not visit before discharge from critical care

Item reduction

In adapting an existing validated measure for use in another culture, there is a tension between the desirability of keeping the instrument in its previously validated form and the need to ensure scale integrity, which might require dropping poorly performing items. The following criteria will be used to tag items for possible removal:

- items with high item non-response rates (>10%), suggesting irrelevance or lack of comprehensibility or acceptability;
- items with poorer discrimination (>70% selecting the lowest or highest category);
- redundant items (item to own-scale Cronbach's alpha of 0.8, corrected for overlap); and
- items measuring a construct other than that intended (component loadings <0.4 in principal components analysis).

Items meeting the above criteria will be discussed with [name] before a final decision on removal.

Factor analysis

Confirmatory factor analytic techniques will be used to test the goodness of fit of the two-factor solution for the FS-ICU developed in the North American validation study.⁸

Reliability analysis

Internal consistency will be evaluated through calculation of item-total correlations and Cronbach's alpha.¹⁶ Item-total correlations <0.4 or Cronbach's alpha <0.8 will be taken as indicative of potential lack of internal consistency.

Validity analysis

The criterion validity of the FS-ICU among family members of non-survivors will be assessed by comparison with the QODD questionnaire.¹⁷ All family members of non-survivors during the first month will be sent a QODD questionnaire along with the FS-ICU. The hypotheses that will be tested are that higher values for the two summary domain scores of the FS-ICU (satisfaction with care and satisfaction with decision-making) are associated with higher values for the overall QODD score, and that scores on four specific items in the QODD (pain control, breathing comfort, care by doctors, care by all providers⁸) will be moderately correlated with FS-ICU scores. No sufficiently well-validated measure exists to conduct a validity analysis of the FS-ICU among family members of critical care survivors.

Main analysis

Family satisfaction will be described by summarising the responses to the 24 individual questionnaire items of the FS-ICU and the two summary domain scores for satisfaction with care and satisfaction with decision-making. Variation in satisfaction across the critical care units will be summarised by presenting the domain scores for each unit, anonymised, in the form of funnel plots,¹⁸ both before and after adjustment for family member, patient and unit/hospital characteristics.

Variation in family satisfaction by: family member characteristics (e.g. relationship to the patient); patient/admission characteristics; unit/hospital characteristics; and other contextual factors will be explored using multilevel linear regression modelling. The outcomes for the regression models will be the two domain scores for satisfaction with care and satisfaction with decision-making. Models will be stratified by the survival status of the patient at discharge from the critical care unit. The levels of the model will be: level 1, family member; level 2, patient/critical care unit admission; level 3, unit/hospital. Family member characteristics entered into the models will include: age; sex; and relationship to the patient. Patient/admission characteristics will include: age; sex; severe chronic conditions in the past medical history; surgical status (elective surgery, emergency surgery, non-surgical); acute severity of illness (ICNARC Physiology Score¹⁹); and length of stay in the critical

care unit. Unit/hospital characteristics will include: teaching status; and number of beds in the critical care unit. Contextual factors will include: month of the year (seasonality). Non-linearity in the relationship between continuous predictors and satisfaction will be modelled using restricted cubic splines.

Variation in family satisfaction by country will be explored by comparing data collected for the FREE study with FS-ICU data from Canada (and available to [name]) in the context of a multilevel linear regression model with a similar structure to that above. Country comparisons will be adjusted for the age, sex and relationship to the patient of the family member and for patient characteristics consistently recorded in the different datasets.

As routinely surveying family members of all patients admitted to a critical care unit would neither be feasible nor cost-effective, understanding the association between patient factors and family satisfaction will enable an appropriately stratified sampling frame to be explored and developed.

A number of potential alternative sampling frames will be constructed based on results of the regression models, and varying the numbers of patients sampled and the timing(s) of the samples within the year. Potential sampling frames include: 100% sampling over a short timeframe; simple random sampling; and random sampling stratified by patient/admission characteristics (e.g. age, sex, survival status, length of stay). The representativeness of the proposed sampling frames will be assessed by assessing the correlation between the FS-ICU domain scores calculated in the sample and in the total population for each critical care unit. Uncertainty in the correlation will be assessed using bootstrapping techniques.

8. Ethical compliance

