The overall aim of the FREE Study is to inform valid, representative and cost-effective future use of the FS-ICU questionnaire into quality improvement programmes for adult critical care services in the NHS in the UK.

The objectives of the FREE Study are:

- to test the face and content validity and the comprehensibility of the FS-ICU;
- to establish the internal consistency, construct validity and reliability of the FS-ICU;
- to describe family satisfaction using the FS-ICU and explore how family satisfaction, measured with the FS-ICU, varies by:
 - family member;
 - patient characteristics;
 - unit/hospital characteristics;
 - other contextual factors; and
 - country (through comparison with FS-ICU data held in Canada);
- to model approaches to sampling to achieve representative sampling for feasible, cost effective future use of the FS-ICU in quality improvement in the NHS.

4. Study design

The FREE Study is a mixed methods study comprising a psychometric evaluation (FREE-Qual) leading to a multicentre cohort study.

The objectives of the FREE Study will be addressed in two sub-studies.

FREE-Qual

FREE-Qual is a qualitative study (see: Section 5) which will address the first objective by testing the face and content validity and the comprehensibility of the validated Canadian FS-ICU. Modifications to the FS-ICU questionnaire will then be made, if required.

The FREE Study

FREE is a multicentre cohort study (see: Section 6) which will address the remaining objectives using the UK adaptation of the FS-ICU questionnaire (FREE-Qual).

Staff at twenty adult, general critical care units will identify up to four family members for consecutive patients admitted to their unit who stay more than 24 hours. Family members who consent to take part will be sent a questionnaire three weeks following patient discharge from the critical care unit.

The recruitment period will be one year, chosen to avoid bias from seasonal variation in case mix and workload. A psychometric assessment of the FS-ICU will be undertaken using data collected during the first month.

5. FREE-Qual

Research Ethics Committee reference:	12/YH/0415
Sponsor reference:	ICNARC/02/05/12
NIHR CRN Portfolio ID number:	112459
Protocol version:	1.0
Protocol version date:	31 July 2012

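### All psychometric analysis is tied to the first month's responses, so neither a revised questionnaire nor the item selection behind it would be confirmed in independent data

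*Protocol*

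**What the plan says.** Protocol section 4 sets the data source: "A psychometric assessment of the FS-ICU will be undertaken using data collected during the first month". Section 7.2 (Psychometric assessment) repeats it, describing returns from family members "recruited during the first month of recruitment (approximately 1000"), and then lists what is done with them: "The analysis will comprise the following steps: descriptive analysis; item reduction; factor analysis; reliability analysis; and validity analysis".

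Item reduction has four criteria: high non-response, floor or ceiling concentration, redundancy, and "items measuring a construct other than that intended (component loadings <0.4 in principal components analysis"). These are screening rules ("The following criteria will be used to tag items for possible removal"), and tagged items go to the instrument's developer before any decision. The factor analysis that follows is to "test the goodness of fit of the two-factor solution for the FS-ICU developed in the North American validation study".

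If substantive changes are needed, "these will be incorporated into a new version of the FS-ICU questionnaire and recruitment and data collection will re-commence" and run for 12 months. The Main analysis part of section 7.2 describes the 24 items and models the two domain scores. It contains no factor, reliability or validity analysis. Section 6.5 restricts the QODD, the criterion measure, to the first month.

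**The concern.** The second study objective is to establish internal consistency, construct validity and reliability of the UK instrument, and section 2 treats knowledge of its measurement properties as a prerequisite for use in NHS quality improvement. One month's data both select the items and supply the evidence on the items retained.

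There are two branches:

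- **Revision.** The version that generates every main result is a new one, and the protocol states no psychometric analysis of the data collected with it. For a version that only loses items, the evidence comes from the responses that chose the items. For reworded or added items there is none.
- **No revision.** The objective is answered from a single month, while the rest of the year's responses to the same items are not used for it. Section 7.1 chose a full year to avoid seasonal bias in case mix and workload, and a one-month assessment does not share that protection.

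**Working it through.** **Size of the first-month data set.** The plan's figure is approximately 1,000. Section 7.1 gives annual inputs; dividing by 12 assumes even monthly returns.

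- Initial calculation: 20 units × 520 × 0.74 = 7,696 patients, rounded to 7,700. Then 7,700 × 2.5 = 19,250 family members, × 0.66 = 12,705 responses, and 12,705 / 12 = 1,059 responses a month.
- Updated calculation: 14,200 / 12 = 1,183 recruits a month. Then 14,200 × 0.60 = 8,520 responses, and 8,520 / 12 = 710 responses a month.

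The stated figure fits initial-plan responses (1,059) or, loosely, updated-plan recruits (1,183). It is not shown to be wrong.

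**Data left unused for the second objective.** With 11 of 12 months remaining: 8,520 × 11/12 = 7,810 responses on the updated inputs, or 12,705 × 11/12 = 11,646 on the initial ones. If responses were independent, standard errors of loadings and correlations from 11 months would be smaller than from one month by a factor of √11 = 3.3. Responses are not fully independent: the updated plan expects 8,500 / 5,500 = 1.5 responses per patient, so analyses should allow for relatives of the same patient.

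**Effect of selecting and testing on the same data.** This was simulated under assumptions not in the protocol: 14 + 10 five-category items, two factors correlated 0.7, independent respondents, 300 repetitions, and automatic removal when the loading on the domain's first principal component is below 0.4. Alpha for the retained items was compared with alpha for the same items in a fresh sample of equal size.

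| Items | n | Dropped per domain | Mean excess in alpha | Decisions per domain that differ in a fresh sample |
|---|---|---|---|---|
| All loadings 0.75 | 500 to 1,058 | 0 | within ±0.0004 | 0 |
| Four per domain at 0.38, rest 0.70 | 500 | 1.7 | 0.005 | 1.9 |
| Same | 708 | 1.7 | 0.004 | 1.9 |
| Same | 1,000 | 1.7 | 0.002 | 1.8 |

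Where all items load well, sharing the data does no harm. Where some are borderline, alpha hardly moves against the protocol's 0.8 threshold, but which items survive depends heavily on the sample. Confirmatory fit indices were not simulated.

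**The two branches side by side.**

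| Outcome of month 1 | Structure and internal consistency | Criterion validity (QODD) |
|---|---|---|
| No change | Month 1 only | Month 1 only |
| Items removed | Retained items, on the data that selected them | Month 1 only, old version |
| Items reworded or added | No test stated | No test stated |

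**The case against.** The strongest reply has four parts.

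1. **The factor analysis is genuinely confirmatory.** It tests a two-factor structure fixed in advance from outside data. Removal is discretionary, and only the loading criterion among the four bears on structure. This stands. A reader might infer that the confirmatory label is empty; the text does not support that. The label is weakened only if items are first removed on loadings from the same responses.
2. **A revised version is not wholly untested.** Factor and reliability analysis are listed after item reduction, so retained items would be examined in the first-month data. Removal is also the only change section 7.2 sets out; rewording and additions belong mainly to FREE-Qual (section 5). This stands for deletion-only revisions, where the gap is independent confirmation. Section 7.2 does not, however, confine substantive changes to deletion.
3. **An early assessment has a purpose, and later re-analysis may sit in the SAP.** An early screen is sensible, and nothing here shows that one month's sample is too small for a 24-item, two-factor model. A SAP, not shown, could add a re-analysis. But the protocol does more than stay silent: it names the data that serve this objective. It also limits the QODD mailing, which an analysis plan alone cannot undo.
4. **The first-month figure is not an error.** A reader might infer that approximately 1,000 should become about 700. That is unsupported: the bracket can mean recruits, and the sample-size update came after the first full quarter, when month 1 was already past.

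It would also be tempting to say that alpha will be materially inflated. The simulation does not bear that out.

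**Conclusion.** The point holds in a limited form. As written, the protocol plans no confirmation, in data not used to choose the items, of the structure or internal consistency of a substantively revised questionnaire, and no test at all of reworded or added items. If nothing is revised, the second objective uses about one twelfth of the responses.

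The revision branch is conditional on substantive changes, and the text does not say whether re-commencement starts a new first month with its own assessment and QODD mailing. If it does, the gap narrows.

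The cost is unreplicated item selection and forgone precision. The figure of about 1.8 differing decisions per domain rests on simulated borderline items and automatic removal; with uniformly good items it is zero. The 7,800 later responses and the factor of 3.3 assume even monthly returns, and the factor also assumes independent responses.

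**What to change.** Keep the first-month assessment as the screen for changing the questionnaire. Add to section 7.2 that two-factor fit, item-total correlations and Cronbach's alpha will be re-estimated on responses not used for item selection: the remaining months if the questionnaire is unchanged, or the 12-month cohort on the new version if it is revised. Use standard errors and fit statistics that allow for relatives clustered within patients, and report these as the main psychometric result for the second objective. Align the data source in section 4.

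State also whether re-commencement brings a new first-month assessment and whether the QODD is re-sent, since criterion validity of a revised version cannot otherwise be examined.

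The re-estimation costs a modest amount of analysis on data already collected, with no extra participants or FS-ICU mailings. Repeating criterion validity would need additional QODD mailings to families of non-survivors.

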Co-ordination of care?

- The teamwork of all the ICU staff who took care of your family member

Excellent 	Very good 	Good 	Fair 	Poor 	N/A 
---------------------------------	---------------------------------	----------------------------	----------------------------	----------------------------	---------------------------

Nurses

Q7

Skill and competence of ICU nurses?

- How well the nurses cared for your family member

Excellent 	Very good 	Good 	Fair 	Poor 	N/A 
---------------------------------	---------------------------------	----------------------------	----------------------------	----------------------------	---------------------------

Q8

Frequency of communication with ICU nurses?

- How often nurses communicated to you about your family member's condition

Excellent 	Very good 	Good 	Fair 	Poor 	N/A 
---------------------------------	---------------------------------	----------------------------	----------------------------	----------------------------	---------------------------

Doctors

Q9

Skill and competence of ICU doctors?

- How well doctors cared for your family member

Excellent 	Very good 	Good 	Fair 	Poor 	N/A 
---------------------------------	---------------------------------	----------------------------	----------------------------	----------------------------	---------------------------

The ICU

Q10

The atmosphere (mood) of the ICU was?

Excellent 	Very good 	Good 	Fair 	Poor 	N/A 
---------------------------------	---------------------------------	----------------------------	----------------------------	----------------------------	---------------------------

The Waiting Room

Q11

The atmosphere (mood) in the ICU Waiting Room was?

Excellent 	Very good 	Good 	Fair 	Poor 	N/A 

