---------------------------------	---------------------------------	----------------------------	----------------------------	----------------------------	---------------------------

Level/amount of health care

(For Q12, please pay attention to the order of the responses)

Q12

Some people want everything done for their health problems while others do not want a lot done. How satisfied were you with the **LEVEL** or **amount** of health care your family member received in the ICU?

Very dissatisfied 	Slightly dissatisfied 	Mostly satisfied 	Very satisfied 	Completely satisfied 
---	---	--	--------------------------------------	--

Family satisfaction with decision making around care of critically ill patients

Instructions for family members of critically ill patients

This part of the questionnaire is designed to measure how you feel about your involvement in decisions related to your family member's health care.

In the Intensive Care Unit (ICU), your family member may have received care from different people. We would like you to think about all the care your family member received when you are answering the questions.

Please tick **one** box that best describes your feelings...

Information needs

Q1

Frequency of communication with ICU doctors?

- How often doctors communicated to you about your family member's condition

Excellent 	Very good 	Good 	Fair 	Poor 	N/A 
---------------------------------	---------------------------------	----------------------------	----------------------------	----------------------------	---------------------------

Q2

Ease of getting information?

- Willingness of ICU staff to answer your questions

Excellent 	Very good 	Good 	Fair 	Poor 	N/A 
---------------------------------	---------------------------------	----------------------------	----------------------------	----------------------------	---------------------------

Q3

Understanding of information?

- How well ICU staff provided you with explanations that you understood

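### The rule in 7.2 for items measuring another construct (PCA loading below 0.4) finds weak items and never compares an item's own domain with the other, so whether it tags a mainly other-domain item depends on an unstated component and rotation

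*Protocol*

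**What the plan says.** Section 7.2 (Item reduction) introduces four criteria with "The following criteria will be used to tag items for possible removal". The fourth is "items measuring a construct other than that intended (component loadings <0.4 in principal components analysis". The text does not say which component is meant, whether the solution is rotated, or whether the analysis is run per scale or on all 24 items. Review depends on being tagged: "Items meeting the above criteria will be discussed with" a named adviser before any decision on removal.

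Two later steps bear on structure. Under Factor analysis, "Confirmatory factor analytic techniques will be used to test the goodness of fit of the two-factor solution for the FS-ICU" from the North American validation. Under Reliability analysis, "Item-total correlations <0.4 or Cronbach's alpha <0.8 will be taken as indicative of potential lack of internal consistency".

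The main analysis then describes "the 24 individual questionnaire items of the FS-ICU and the two summary domain scores for satisfaction with care and satisfaction with decision-making". The two domain scores are also the outcomes of the multilevel models and the quantities in the unit funnel plots. Section 2 counts tests of discriminant validity among the minimum standards for a cross-cultural adaptation.

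**The concern.** The purpose of the criterion and its test do not match. A loading below 0.4 says that an item is weakly related to a component. An item that belongs to the other domain need not be weak. Both domains are rated by the same person about the same stay, so they are likely to be correlated, and such an item can then load well above 0.4 on the component it is judged against. Telling the two cases apart needs a comparison of own-domain with other-domain association, and 7.2 has none at item level.

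The first-month assessment is the planned check of the imported two-domain structure before the year's data are scored on it. Appendix 1 shows why the question is practical. Care item Q8 asks "How often nurses communicated to you about your family member's condition", and decision-making item Q1 asks "How often doctors communicated to you about your family member's condition". The two differ only in the professional named but are scored in different domains. That is a reason to test the placement and no evidence that it is wrong.

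**Working it through.** The plan gives no figure to reproduce, so the check is how the rule behaves on an item known to be misplaced.

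**Inputs.** From the protocol: 24 items, counted in Appendix 1 as 14 care (Q1 to Q12, with Q2 in three parts) and 10 decision-making (Q1 to Q10); cut-offs of 0.4 for loadings and for item-total correlations; about 1,000 family members in the first month. Assumed, because the protocol gives neither: factor loading L = 0.7 (range 0.6 to 0.8) and domain correlation r = 0.3 to 0.9. One care item is made to load only on decision-making.

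**Item-total correlation, corrected for overlap.** With 13 genuine care items:
- own domain = 13·L²·r / √(13 + 13·12·L²) = 6.37r / √89.44 = 0.674r
- other domain = 10·L² / √(10 + 10·9·L²) = 4.90 / √54.10 = 0.67

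The own-domain value reaches 0.4 at r = 0.4/0.674 = 0.59. At higher r the item-total check no longer flags the item (at L = 0.6 and 0.8 the crossing is near r = 0.7 and 0.5).

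**Own-scale component, r = 0.7.** The 13 genuine items correlate 0.49 with each other and 0.343 with the misplaced item. The largest eigenvalue solves (6.88 − e)(1 − e) = 0.343 × 4.459, giving e = 7.13. The misplaced item's weight is 0.198, so its loading is 0.198 × √7.13 = 0.53.

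**All readings, L = 0.7.**

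| r | Own-scale component | First unrotated component, 24 items | Varimax, intended component | Item-total, own | Item-total, other |
|---|---|---|---|---|---|
| 0.5 | 0.39 | 0.60 | 0.17 | 0.34 | 0.67 |
| 0.6 | 0.46 | 0.62 | 0.21 | 0.40 | 0.67 |
| 0.7 | 0.53 | 0.65 | 0.25 | 0.47 | 0.67 |
| 0.8 | 0.60 | 0.67 | 0.29 | 0.54 | 0.67 |
| 0.9 | 0.66 | 0.69 | 0.34 | 0.61 | 0.67 |

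In 1,000 simulated samples of n = 1,000, the own-scale reading tags the item in 69%, 3%, 0% and 0% of samples at r = 0.5, 0.6, 0.7 and 0.8. The intended varimax component tags it in 100% at each r. Reading the rule as below 0.4 on every component tags it in 0%. The first unrotated component stays above 0.4 for every r from 0.3 to 0.9 and every L from 0.6 to 0.8.

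**Item loading on both domains, mainly the other.** With factor loadings of 0.3 (own) and 0.5 (other), varimax gives 0.42 to 0.52 on the own component and 0.59 to 0.60 on the other over r = 0.5 to 0.9, so the item is not tagged. An oblique rotation gives 0.31 on its own component at r = 0.5 and 0.7, so it is tagged. Its corrected correlations, own against other, are 0.53 and 0.62 at r = 0.5, and 0.72 and 0.73 at r = 0.9.

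**CFA with one wholly misplaced item.** Degrees of freedom: 24·25/2 − (24 + 24 + 1) = 251. At r = 0.7 and N = 1,000 the noncentrality is 300, so RMSEA = √(300/(251 × 1,000)) = 0.035, with CFI 0.974. At r = 0.8, RMSEA is 0.028 and CFI 0.983.

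**The case against.** A reader might infer that the rule always fails and that a misplaced item stays in the wrong score. The documents do not support that. The bullet speaks of the intended construct, which points naturally to the intended component of a rotated two-component solution. On that reading a wholly misplaced item is tagged almost always; the exception is r near 0.9 with loadings of 0.8, where the varimax value is 0.40 to 0.41. The criterion also only prompts discussion, and a CFA follows.

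Three further arguments deserve weight.
- The section calls its methods brief and says that they mirror the North American study, so component and rotation may be set there or in a SAP. That excuses the missing detail. It does not excuse the criterion, because the protocol fixes the number and the number does not measure what the bullet names.
- An item-reduction screen need not allocate items to domains; that is the CFA's task. In part this stands. An exact-fit chi-square would react: at r = 0.7 and N = 1,000 its expected value is about 251 + 300 = 551 on 251 degrees of freedom. Item-level CFA output could also point to the item. But the stated target is goodness of fit, global indices can look acceptable, and none of them names an item.
- The domain correlation and loadings are assumed, and no effect on a domain score, regression coefficient or funnel plot has been shown. This stands. At r = 0.5 or below, the own-scale reading often or usually tags the item when loadings are 0.7.

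**Conclusion.** The concern holds in a conditional form. The fourth criterion detects weak items, and 7.2 contains no comparison of an item's association with its own and the other domain. Whether an item belonging mainly to the other domain is tagged depends on choices that the text leaves open. The intended component of a rotated solution catches a wholly misplaced item. An own-scale component misses it at domain correlations of about 0.6 or more, and the first unrotated component misses it throughout the range tried. Varimax also misses a cross-loading item of the 0.3 against 0.5 kind. The remaining checks are not a dependable second net, so such an item can remain in its domain score without planned review.

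The sizes rest on a two-factor model with assumed loadings of 0.6 to 0.8 and domain correlations of 0.3 to 0.9. They do not show that any FS-ICU item is misplaced, or that a study result would change. The case for acting is that the correction is cheap and supplies the item-level discriminant check that the protocol's own background section calls for.

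**What to change.** In 7.2, replace the fourth criterion with two tags:
- weak item: loading below 0.4 on the intended component of a two-component solution of all items, with the rotation named;
- possible other-domain item: correlation with the other domain score equal to or higher than the correlation with its own domain score, corrected for overlap.

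Both send the item to discussion and neither removes it automatically, so the aim of preserving the validated form is respected.

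The other-domain correlation was the larger in every misplaced-item case run (r = 0.3 to 0.9, loadings 0.6 to 0.8) and for the 0.3 against 0.5 item at r = 0.5 to 0.9. In simulated five-category data (n = 700, loadings 0.7, r = 0.6 to 0.9), the comparison tagged the misplaced item in 99.5% to 100% of runs and falsely tagged under 1% of correctly placed items.

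The cost is a reworded criterion, one more column in the item table, and possibly one or two more items to discuss. No new data are needed.
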